6.3.1 Study Schedule

Assessment Points	Baseline	during rx 1-Month	during rx 2-Month	POST rx 3-Month
Medical History, Height, MINI Psychiatric Interview, Demographics (i.e., sex, race)	■			
EDE-BSV Interview, Treatment Credibility/Satisfaction	■			■
EDE-Q-I, FCI, PHQ-9, GPAQ, Weight, Adverse Events, Compliance	■	■	■	■

6.3.2 Informed Consent

Research clinicians (who have completed IRB and ethics training) will meet with potential participants to discuss the study and all procedures, treatments, and risks and obtain written informed consent. All potential participants will be free to decide whether or not to participate and are free to withdraw from the study at any time. Alternative treatments (both psychosocial and pharmacological options) will be discussed and referrals offered if requested. The written informed consent will be obtained after opportunity to discuss and address all questions. A copy of the signed informed consent form will be given to the participants and the original will be kept in the participant's file. A decision to not participate or to discontinue participation would not adversely influence future interactions with Yale, Yale School of Medicine, or the investigative group. The process of informed consent may be completed in-person or remotely. If completed remotely, the consent process will be conducted by one of two methods: 1) a consent form will be mailed or emailed to the participant. The participant will then mail back (or email back) the signed consent form to the study team for signature or 2) the consent form will be completed using the validated Part 11 version of REDCap. A copy of the final consent (signed by both parties) will be mailed or emailed to the participant for his/her records. For all consenting, a meeting will be held in-person or remotely (e.g., via Zoom) to discuss the study and informed consent process.

6.3.3 Screening

Pre-Screening: Participants responding to recruitment efforts will be screened by telephone. If participants prefer to answer some of the screening questions through the Yale Qualtrics system, participants will indicate their consent to the recruitment/screening process in the online system. Potentially eligible participants will be consented and evaluated in-person or remotely by trained supervised research clinicians (doctoral level and/or advanced trainees).

6.3.4 Recruitment, Enrollment and Retention

Participants will be recruited from the Yale Bariatric/Gastrointestinal Surgery Center of Excellence via flyers and posters at the bariatric center, provider referral, and patient mailings. Specifically, the bariatric team agreed to identify potential subjects during routine medical post-surgical evaluations and support group meetings. In addition, flyers and posters alerting potential subjects to the treatment study will be placed in the Yale Gastrointestinal Surgery/Bariatric Center. Flyers will also be placed on our program's website. Letters will be mailed to individuals who had MBS within the past five years at Yale. For the mailing, we will utilize the Yale Joint Data Analytics Team (JDAT) to identify potential subjects. JDAT creates updated list of individuals who have recently had bariatric surgery at Yale and ensures that letters are not sent to subjects who have opted out of research at Yale. Yale JDAT is able to identify potential subjects by specific parameters related to inclusion criteria such as age (18-65), and MBS (laparoscopic Roux-en-Y gastric bypass or sleeve gastrectomy) performed at Yale. A study flyer and letter describing the study (approved by the Yale IRB) will be mailed. If interested, individuals will have the opportunity to contact the study team for screening. *Previous experience with this recruitment process has been very successful and without adverse reactions (i.e., for NIH/NIDDK-funded bariatric trial R01 DK098492).* Participants who opted out of research will not be contacted.

Advertisements will ask participants to contact our research team if they are interested in the study. When potential participants call and/or respond to an online form, they will be screened to determine whether they are likely to be eligible. If they seem potentially eligible and interested, they will be scheduled for an initial in-person or remote (e.g., via Zoom) assessment.

After initial contact, research clinicians (who have completed IRB training) will meet with potential participants to discuss the study, the treatments, the assessments, the follow-up period, and the informed consent procedures and forms. Clinicians will answer any questions and obtain written informed consent. A copy of the signed informed consent form will be given to the participants and the original will be kept in the participant's file. All potential subjects and/or participating participants are free to decide whether or not to participate and are free to withdraw from the study at any time. Alternative treatments would be discussed and/or referrals provided. A decision not to participate or to discontinue participation would not adversely affect future interactions with Yale or the Yale School of Medicine.

6.3.5 On Study Visits.

Participants may attend visits in-person at the Yale Program for Obesity, Weight, and Eating Research or remotely.

6.3.6 End of Study and Follow-up

Participants will be asked to attend a post-treatment (end of study) assessment, which will consist of an interview, measured weight, and completion of self-report surveys as indicated in the assessment schedule grid.

6.3.7 Removal of subjects

Withdrawal/attrition from treatments will be examined. Use of other treatments during the study will be assessed and considered in analyses. Patients will be asked about all forms of treatments during major assessments. Criteria for removal of patients from the study may include worsening depression, suicidal ideation, or failure to comply with medication. Previous experience suggests that worsening clinical status is rare; in such cases, [name] and study physician would determine whether to remove the person from the study and provide referrals.

6.4 Statistical Method

6.4.1 Statistical Design and Analyses

To examine weight changes, we will examine percent total weight loss for the entire participant group. We will also compare percent weight loss for the two responder groups. We will use linear mixed effects models with treatment (BWL or BWL+NB medication), time and the interaction between treatment and time to examine percent weight loss. We will construct a 95% confidence interval for percent weight loss within the non-responder arm based on the mixed model above.

7 - Trial Administration

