4.1 Hypothesis

We hypothesize that the treatments will be feasible and acceptable to subjects, and that subjects will experience significant weight loss and improvements in psychosocial functioning. More specifically, it is hypothesized that early responders to BWL will show weight loss during the trial, while the addition of NB will aid early non-responders in achieving weight loss.

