5.2 Outcome Variables

5.2.1 Primary Outcome Variables

Primary outcomes will include: 1) feasibility, 2) acceptability, and 3) weight loss.

- 1) Feasibility will be determined by examining enrollment, number of sessions attended, compliance, and retention.
- 2) Treatment credibility and satisfaction will be examined via self-report.
- 3) To examine weight changes, we will examine percent total weight loss for the entire participant group. We will also compare percent weight loss for the two responder groups.

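### Two unranked primary weight analyses leave the weight hypothesis without a deciding result, and the responder comparison cannot serve as a primary test because its groups are selected on part of the outcome

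*Combined protocol and SAP*

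**What the plan says.** Section 5.2.1 (repeated in the Synopsis) states: "Primary outcomes will include: 1) feasibility, 2) acceptability, and 3) weight loss". Under weight loss it places two analyses without ranking them: "we will examine percent total weight loss for the entire participant group", and then "We will also compare percent weight loss for the two responder groups".

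Section 6.4.1 is the whole statistical section. It repeats both analyses, "we will examine percent total weight loss for the entire participant group. We will also compare percent weight loss for the two responder groups", and gives the model: "We will use linear mixed effects models with treatment (BWL or BWL+NB medication), time and the interaction between treatment and time". It closes with a further result that section 5.2.1 does not list: "We will construct a 95% confidence interval for percent weight loss within the non-responder arm based on the mixed model above".

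The hypothesis in section 4.1 is that "subjects will experience significant weight loss and improvements in psychosocial functioning". It then makes separate predictions for early responders and for non-responders given NB.

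Section 6.2 computes %TWL from initial pre-treatment weight to post-treatment weight, and the schedule in section 6.3.1 labels Month 3 as post-treatment. Groups are not randomised: section 6.3 assigns them by weight loss after one month of behavioural treatment. No section states a significance level, a deciding coefficient, a success criterion or an order among the weight results, or calls any of them descriptive.

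**The concern.** The two listed analyses answer different questions. Whole-group %TWL asks whether participants lost weight. The responder comparison asks whether one self-selected group lost more than the other. As both are primary and neither leads, the report could present either as the primary weight finding.

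The second is the more serious problem. Responders are, by definition, those who had already lost more weight at Month 1. That loss remains in their Month-3 %TWL because the formula starts at pre-treatment. A group difference is therefore built in before NB is given. If NB then helps non-responders, they catch up and the difference narrows. A significant result is thus most likely when NB does nothing, which is the reverse of what a reader would expect from a comparison labelled treatment in the model.

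Sections 1.1, 2.1 and 3.2 say that the results will supply effect sizes for larger trials. A group difference produced by selection would be a poor basis for that.

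**Working it through.** **No figure to reproduce.** The only design number is N=25 (section 5.3.1), given without derivation. There is no SD, effect size, power or significance level.

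**Inputs from the documents.** N=25. Groups are set by Month-1 loss, and the outcome runs from pre-treatment to post-treatment. The trial's response cut-off is not fixed; the early-weight-loss paragraph of section 2.1 cites at least 1% from earlier work.

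**Assumptions, not in the documents.** A 1% cut-off; normal weight changes; the SDs, means and correlations below; no dropout; t-tests at Month 3, two-sided 5%, standing in for the mixed-model contrasts.

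**Step 1. Difference built in by selection.** Let Month-1 loss have mean m1 and SD s1, Month-3 %TWL have SD s3, and their correlation be r. With c = (1 − m1)/s1 and P = 1 − Φ(c), the share of responders:

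- Month-1 gap = s1 × [φ(c)/P + φ(c)/(1 − P)]
- Month-3 gap = r × (s3/s1) × Month-1 gap − NB effect

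Take zero mean loss at both months and no NB effect.

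- *Setting A*: s1 = 1.5, with later change independent and SD 3. Then s3 = √(2.25 + 9) = 3.35 and r = 1.5/3.35 = 0.45. c = 0.667, φ(c) = 0.319, P = 0.252. Month-1 gap = 1.5 × (1.27 + 0.43) ≈ 2.5 points. The multiplier r × s3/s1 is 1.0, so the Month-3 gap is also about 2.5 points.
- *Setting B*: s1 = 1.8, s3 = 4, r = 0.6. c = 0.556, φ(c) = 0.342, P = 0.289. Month-1 gap = 1.8 × (1.18 + 0.48) ≈ 3.0 points. The multiplier is 0.6 × 4/1.8 = 1.33, so the Month-3 gap is about 4.0 points.

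No treatment produced either gap.

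**Step 2. How often this is significant.** In simulated trials of 25, the responder comparison is significant in 37% to 38% of trials in setting A (across repeated runs) and 66% in setting B. In a 20,000-trial run of each setting, every significant result favoured responders to the reported precision. The whole-group test keeps its 5% two-sided error.

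**Step 3. What happens as NB works.** Now let mean loss be 0.67 points at Month 1 and 2 points at Month 3 without NB, with s1 = 1.8, s3 = 4 and r = 0.6. The selection gap is 1.33 × 2.89 = 3.85 points. Non-responders would lose 0.36 points on average without NB. Ranges are across repeated runs.

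| NB effect (points) | True group gap | Responder comparison significant | True non-responder loss | Non-responder interval above zero | Whole group significant |
|---|---|---|---|---|---|
| 0 | 3.85 | 71% to 72% | 0.36 | 5% to 6% | 67% |
| 1 | 2.85 | 45% to 47% | 1.36 | 27% | 90% |
| 2 | 1.85 | 22% to 23% | 2.36 | 62% to 64% | 98% |

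The comparison moves against NB benefit, while the non-responder interval moves with it. The first row also shows that the whole-group result is significant in 67% of trials when NB adds nothing, so it cannot stand as evidence for NB.

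**Dropout.** Dropout lowers these rates without removing the cause. In one example (Month-1 mean 1, SD 1.5; both groups lose 2 more points, SD 3), the responder comparison is significant in 43% of complete trials and about 30% with 30% dropout, the lower end of the 30% to 45% that section 7.12 reports for NB studies.

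**The case against.** The strongest reply is that this is a single-site, unrandomised pilot. Section 4.2 makes feasibility and acceptability the primary objective, and no significance level or confirmatory claim is stated. Section 4.1 attaches significant weight loss to participants as a whole, so the whole-group analysis is the natural reading, and the non-responder result is planned as an interval, not a test. Much of this stands. It limits the consequence to reporting and interpretation, and it argues against a formal testing sequence. It does not remove the point: section 5.2.1 still makes the responder comparison primary, section 4.1 predicts a significant loss, and section 7.12 speaks of power to detect differences in the primary outcomes.

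It could also be said that a model contrast measured from Month 1 would avoid carrying the selecting loss forward. In setting A it would, but section 6.2 measures from pre-treatment and section 6.4.1 names no other origin.

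Several stronger readings are tempting but not supported:

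- *Three contrasts share primary status.* Only two are listed as primary; the non-responder interval is unlabelled.
- *The time point is wholly open.* The formula in section 6.2 points to Month 3, although the same section mentions several time points and the model includes time. Counting each contrast at three months as a separate primary test is not justified.
- *A standard family-wise error rate for three tests applies.* Such a rate assumes a 5% null error for each, which the responder comparison does not have.
- *The results routinely disagree.* The documents do not show this. In simulation, the share of complete-data trials in which the three results were not all alike ran from 27% to 99% depending on assumptions, and part of that is different questions correctly receiving different answers.

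**Conclusion.** The point holds. Two primary weight analyses are unranked, a non-responder interval is added without a stated role, and no result is named as deciding the weight hypothesis. The responder comparison should not be a primary test. With zero mean loss and no NB effect it is significant in roughly 38% to 66% of simulated trials, and it weakens as NB helps more.

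The percentages depend on the assumed cut-off, SDs, correlation and complete follow-up. The mechanism needs only that Month-1 loss both defines the groups and correlates positively with the final outcome. These are not false positives in the strict sense, since the selected groups do differ; the error would be to read that difference as a treatment effect.

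The plan should be corrected, but the trial is not invalidated: the whole-group estimate and the non-responder interval remain usable for what each describes.

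**What to change.** In sections 5.2.1 and 6.4.1, and in the matching Synopsis entry:

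1. Name whole-group %TWL from baseline to Month 3, with its 95% confidence interval, as the one primary weight estimate.
2. Report the non-responder 95% interval as a supporting estimate, not conditional on the whole-group result.
3. Label the responder versus non-responder comparison, and all Month-1 and Month-2 weight results, descriptive, with no significance claim. Say why for the comparison: its groups are formed on Month-1 loss, which is part of the outcome.
4. State that the whole-group result does not by itself show that NB helped non-responders.

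The cost is a few sentences, with no new data or participants. The small downside is that a favourable group comparison or non-responder interval can no longer stand alone as the primary weight claim.

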Collectively, the lack of evidence-based treatments after MBS remains a critical and concerning gap in the field. An evidence base is urgently needed to direct the field in managing obesity after surgical intervention. Given that BWL and NB are both empirically-based weight-loss treatments, the proposed study will pilot the feasibility and acceptability of delivering behavioral treatment (BWL) to adults struggling with weight regain after MBS. Early weight loss responders will continue with BWL for the duration of treatment, while early non-responders will be given NB as an adjunct to BWL. The pilot will also examine whether augmenting behavioral treatment with NB results in weight loss and improvements in psychosocial functioning. These data will inform designs and provide effect size data to power larger definitive trials examining stepped care approaches with behavioral and pharmacological interventions for post-MBS.

3 - Rationale/Significance

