6.1.2 Dosage, Admin, Schedule (if applicable)

NB Pharmacotherapy Treatment Protocol. Participants who do not respond to the first month of BWL treatment will have NB added to their treatment for the remaining two months of treatment. NB medication will comprise naltrexone (50 mg/day) combined with bupropion (300 mg/day) taken daily. In a previously conducted pilot study, the NB final dosage consisted of 50 mg/day naltrexone combined with 300 mg/day bupropion XL, which closely approximates the newly approved NB combination (Contrave) dosage for weight loss [Greenway et al., 2009; Greenway, Fujioka & Plodkowski, 2010; Smith et al., 2013; Wadden et al., 2011], but with advantages. One advantage is that the formulations of both medications used in this study are already available at substantially lower cost than Contrave (75% savings for retail purchase) and the smaller size of pills (in blinding) is better for patients following MBS. Importantly, the immediate release (IR) version of Bupropion will be used in the present study as recommended by clinical guidelines for MBS populations. Because MBS can lead to changes in medication absorption due to alterations of gut anatomy, clinical practice guidelines recommend avoiding extended-release formulations of medications and using immediate release formulations (de Sousa Prado Geraldo et al., 2014; Lorico, 2020, Vouri et al., 2021). Additionally, using normal-release naltrexone rather than the sustained release formulation available only in Contrave is not seen as a pharmacokinetic disadvantage in any way. Despite a short initial serum half-life, the pharmacologic activity of naltrexone is long-lived, with an effective half-life of over 3 days, consistent with the terminal phase of plasma clearance [Lee et al., 1988]. For this reason, naltrexone has been used effectively in clinical treatment using daily or less frequent dosing.

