6.1.4 Blinding and Procedures for Unblinding (if applicable)

Participants will not be blind to behavioral and medication treatments. There is no placebo for this trial because NB is an evidence-based weight loss treatment.

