6.2 Assessments

Assessment Procedures. **Table 1** summarizes the assessment schedule and measures. Assessments will be done by *independent* evaluators *not* involved in the treatment delivery and *blind* to early weight loss responder status.

Assessment of Treatment Outcome and Time Course.

Percent total weight loss (%TWL) (measured weight across time points). Per standard reporting guidelines, %TWL will be determined by the following formula: [(Initial Pre-Treatment Weight) — (Post-Treatment Weight)] / [(Initial Pre-Treatment Weight)]*100.

Psychosocial/Behavioral Functioning listed below.

Informed consent will be obtained after complete study description, followed by interviews and surveys.

Interviews:

Eating Disorder Examination Interview — Bariatric Surgery Version (EDE-BSV) (18) an investigator-based interview will be the primary method for assessing loss-of-control eating, as well as severity of eating-disorder psychopathology.

Mini International Neuropsychiatric Interview-Version 7.0 (MINI) (19) is a brief structured interview for psychiatric disorders, which will provide data to characterize subjects.

Anthropometrics: **Weight** and **height** will be measured to calculate body mass index.

Self-Report Measures (baseline and repeated per Table 1):

Demographics: ethnicity/race, age, sex, education, and socio-economic status.

Eating Disorder Examination-Questionnaire Version with Instructions (EDE-Q-I) (20), which generates the same eating behavior and pathology data as the interview version, will be used across *all assessment points* given its low burden (*in addition to the EDE-BSV given during major assessment points*).

Food Craving Inventory (FCI) (21) assesses general and specific food cravings (**relevant for NB**) and comprises four subscales for different food groups. The FCI has been validated and psychometrically supported in studies with obesity and BED. The use of this craving instrument will allow direct comparison to the leading NB non-surgical obesity trials (14).

Patient Health Questionnaire-9 (PHQ-9) is a brief and widely-used measure of depression in diverse medical settings (22). Post-MBS depression was associated with poorer MBS outcomes in some studies and is relevant to the study medication.

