6.2.3 Pharmacokinetics (if applicable)

6.2.4 Biomarkers (if applicable)

6.3 Study Procedures

Subjects will participate in an initial evaluation to determine eligibility. Eligible participants who provide written informed consent will start BWL treatment which last for three months. The BWL treatment is a mixture of the published LEARN behavioral lifestyle weight control treatment developed by Brownell (2000) and the Diabetes Prevention Program (Knowler et al., 2002); the PI and research team has extensive experience administering BWL with patients with obesity, binge-eating disorder, and histories of bariatric surgery. BWL will be delivered weekly by research-clinicians according to treatment manuals that detail session-by-session procedures. These manuals closely parallel patient-version BWL self-care materials for the entire course of treatment and follow closely that used by Wadden et al. (2011) in the COR-BMOD Trial testing BWL and NB/placebo medication for obesity, but modified for post-MBS patients. Behavioral strategies (goal-setting, self-monitoring, stimulus control problem-solving) will be taught within a lifestyle approach for achieving dietary goals (augmented by portion size and caloric goals) and physical activity goals (to achieve 180 min/week of moderate physical activity). Research-clinicians will be trained in BWL by the research team and will be supervised and monitored over the course of treatment delivery to ensure quality adherence. After one month of BWL treatment, "treatment response" will be determined based on early weight loss status because of its strong prognostic significance for optimal weight loss outcomes. Early weight-loss responders will continue BWL treatment, while *non*-responders will be given a pharmacologic agent (NB) to augment BWL treatment for the remaining two months of treatment. Outcomes assessments will be done by independent evaluators not involved in the treatment delivery and blind to responder status. Participants will be asked to complete self-report surveys at the baseline evaluation, monthly during treatment, and at the end of treatment. For participants starting NB medication, they will be asked to have labs drawn to examine liver values for safety before starting medication and again after being on the medication for one month.

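### The treatment factor in the 6.4.1 mixed model is month-1 responder status by another name, so its terms cannot estimate the effect of NB or test whether NB augments BWL

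*Combined protocol and SAP*

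**What the plan says.** **Allocation.** The closing paragraph of section 2.1 gives the rule: "Early weight loss responders will continue with BWL for the duration of treatment, while early non-responders will be given NB". Section 6.1.2 repeats it for the drug: "Participants who do not respond to the first month of BWL treatment will have NB added to their treatment". Section 6.1.3 (randomisation) reads NA. Section 6.1.4 adds: "There is no placebo for this trial because NB is an evidence-based weight loss treatment". Section 6.3 says early weight loss was chosen as the criterion "because of its strong prognostic significance for optimal weight loss outcomes".

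**Analysis.** Section 5.2.1 lists this under the primary outcomes: "We will also compare percent weight loss for the two responder groups". Section 6.4.1 repeats that sentence, specifies "linear mixed effects models with treatment (BWL or BWL+NB medication), time and the interaction between treatment and time to examine percent weight loss", and ends: "We will construct a 95% confidence interval for percent weight loss within the non-responder arm based on the mixed model above". The section thus moves from responder groups to treatment to non-responder arm for one and the same split.

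**Outcome.** Section 6.2 defines %TWL as loss from pre-treatment weight ("Per standard reporting guidelines, %TWL will be determined by the following formula"). The schedule in 6.3.1 has weight at baseline and months 1, 2 and 3.

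**Stated use.** Sections 1.1 and 3.2 say the study will compare the two treatment conditions and look at within-group change in the combined condition, and that the data will supply effect sizes for powering definitive trials. Sections 4.2 and 5.1 say repeated assessments will examine whether the combination augments behavioural therapy.

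**The concern.** An effect of NB needs non-responders who did not get NB, or some other basis for saying what they would have lost on BWL alone. The plan has neither, and 6.4.1 states no assumption that would stand in for one. A coefficient labelled treatment then reports how early non-responders differ from early responders, plus whatever NB adds, in unknown proportions.

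The stake is interpretation and planning. The group comparison is a listed primary outcome and is described next to effect sizes for later trials. Read as a drug effect, it could make a useful drug look inert or harmful at month 3. The interaction could mislead in either direction.

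**Working it through.** The plan gives no figure to reproduce: N=25 (section 5.3.1) comes without effect size, SD, alpha or power.

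**1. Aliasing (no assumed values).** With months 1, 2 and 3 as a factor, treatment and treatment-by-time, the fixed-effects matrix has 6 columns and rank 6. Adding responder status and responder-by-time gives 9 columns and still rank 6. No responder term can be estimated beside the treatment terms.

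**2. Size and direction when NB does nothing.** All inputs here are assumed. Section 2.1 cites early-loss values of 0.5 to 3% and at least 1%, but no cut-off is set for this trial.

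- Observed %TWL at month t is y_t = a + (f_t - 1)b + error. Here a is the month-1 rate, b the later rate (same mean μ and SD σb, correlation ρ), and f_t a time factor.
- Grid of 32 cells: μ 1.0 or 1.5%; σb 0.75 or 1.0; total error SD σe 0.7 or 1.0; cut-off c 0.5 or 1%; (f_1, f_2, f_3) = (1, 2, 3) or (1, 1.5, 2).
- Each cell is run with independent visit errors, or with half the error variance shared across visits (the baseline weighing error), and with ρ = 1 or 0.5.
- Non-responder: y_1 < c.

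Let s² = σb² + σe², z = (c - μ)/s and p = Φ(z). By normality:

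- month-1 gap: G = s·φ(z)/[p(1 - p)]
- difference at month t, BWL+NB minus BWL: d_t = -G·cov(y_t, y_1)/s², with cov(y_t, y_1) = σb²[1 + ρ(f_t - 1)], plus σe²/2 for t > 1 if error is shared; d_1 = -G
- interaction, months 1 to 3: (d_3 - d_1)/2
- interaction with a baseline row (0 for everyone): (-0.5d_1 + 0.5d_2 + 1.5d_3)/5

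On complete data a random-intercept mixed model reproduces these mean contrasts. Three cells give the ends of every range:

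| | A | B | C |
|---|---|---|---|
| μ, σb, σe, c | 1.0, 0.75, 1.0, 1.0 | 1.5, 1.0, 0.7, 0.5 | 1.5, 0.75, 1.0, 0.5 |
| f_2, f_3; ρ | 1.5, 2; 0.5 | 2, 3; 1 | 1.5, 2; 0.5 |
| error | independent | half shared | independent |
| s²; p | 1.5625; 0.50 | 1.49; 0.206 | 1.5625; 0.212 |
| d_1 = -G | -1.995 | -2.126 | -2.168 |
| cov(y_3, y_1)/s² | 0.84375/1.5625 = 0.54 | 3.245/1.49 = 2.178 | 0.54 |
| d_3 | -1.08 | -4.63 | -1.17 |
| slope, baseline row in | -0.21 | -1.50 | -0.23 |
| slope, months 1-3 | +0.46 | -1.25 | +0.50 |

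The month-3 difference is negative in every cell, because it takes the sign opposite to the correlation between month-1 and month-3 loss. The months 1 to 3 slope favours NB whenever σb²ρ(f_3 - 1) is less than the visit-specific error variance (σe², or σe²/2 if half is shared). At ρ = 0.5 that holds in 4 of 32 cells with shared error and 16 of 32 with independent error. A further 4 cells in each set are exactly zero, and simulation scatters those to either side (it counted 5 and 18).

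**3. A true benefit of +2 points at month 3** (+1 at month 2, none at month 1) adds 2 to d_3, (2 - 0)/2 = 1 to the months 1 to 3 slope, and (0.5×1 + 1.5×2)/5 = 0.7 to the slope with baseline. The month-3 difference then runs from -2.63 (B) to +0.92 (A), and the months 1 to 3 slope from -0.25 (B) to +1.50 (C). Neither reliably returns its true value of +2 or +1.

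**4. The non-responder interval.** In cell A with inert NB, mean month-1 loss in non-responders is 1 - 1.25×0.3989/0.5 = 0.003. The month 1 to 3 change is then 0.82 from continued BWL (1 - 0.18×0.997) plus 0.64 from regression to the mean (0.997/1.5625), or 1.46 points with no drug effect. Across the grid at ρ = 1, simulated trials of N=25 gave a 95% interval for month-3 %TWL wholly above 0 in 4 to 89% of trials.

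**The case against.** **It is a pilot, and the lead objective is feasibility and acceptability.** This stands: those outcomes and whole-group %TWL are untouched, and no decision rule hangs on the treatment term. But supplying effect sizes for later trials is also a stated purpose, so the status of this contrast matters.

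**The basis of the groups is disclosed.** Also true. Sections 5.2.1 and 6.4.1 speak of responder groups, and 6.1.3 and 6.1.4 are open about no randomisation and no placebo. A reader should not infer concealment. What is missing is a statement that the term called treatment is not a treatment effect.

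**The bias need not run against NB.** A reader might infer that the analysis will always hide a benefit. The documents do not support that for the interaction. Section 6.4.1 does not say whether a baseline row, zero for everyone by the 6.2 formula, enters the model, and nothing is said about how far early loss rates persist. For months 1 to 3 the sign is open. For the same reason, a false-positive rate for NB looking worse that assumes a baseline row should not be attributed to this plan.

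**Augmentation is not tied to this contrast.** Sections 4.2 and 5.1 say only that assessments will examine whether the combination augments BWL; they do not promise to demonstrate it or name this model term. The 4.1 hypothesis predicts that NB will help non-responders, not that they will outdo responders. This stands, but 6.4.1 offers no other analysis that could answer the question.

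**Planning could use the arm-level data.** Means and SDs within each pathway are fair inputs for a stepped-care trial. The between-group difference as an NB effect size is not.

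**Some non-responders may not take NB.** That arises after allocation and gives no valid comparator.

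**Conclusion.** The point holds. As planned, treatment and month-1 response are one variable, and no term in the 6.4.1 model isolates NB. That rests on the allocation rule alone.

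The sizes are illustrations on assumed means, SDs, cut-offs and persistence. With no NB effect the month-3 difference is about -1.1 to -4.6 points, so it is biased against NB; that direction follows if early loss is prognostic, as the protocol says. The interaction is biased by about -1.5 to -0.2 points per month with a baseline row and -1.3 to +0.5 without, so no direction can be claimed for it. A lower limit above 0 for non-responders would not show that NB helped. The problem is one of labelling and permitted inference, and it does not invalidate the pilot.

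**What to change.** 1. In 6.4.1, label the factor month-1 response status (responders: BWL; non-responders: BWL+NB), and report its main effect and time interaction as a descriptive comparison of responder groups.
2. State in 6.4.1, with a matching clause in 1.1 and 3.2, that this contrast is not an estimate of the NB effect, will not be used as the NB effect size for later trials, and does not test augmentation.
3. Report the non-responder 95% interval for the month 1 to 3 change beside the change from baseline. Label both uncontrolled, and note that the former includes continued BWL loss and regression to the mean.

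The cost is a few sentences, with no new data, visits or arm. The pilot gives up a between-group effect size, but one that its design cannot identify.
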